11.1 Adverse Event and Serious Adverse Event Recording and Reporting

All AEs (except non-serious AEs for screening failures) that occur after the signing of informed consent and up to 30 days after last drug administration will be recorded in the eCRF and in the patient’s medical records, whether or not considered by the investigator to be related to the study drug. Thereafter only AEs assessed as related should be recorded. All AEs should be recorded using acceptable diagnoses, if possible. For screening failure patients the non-serious adverse events will not be recorded in the e-CRF but only in the patient’s medical records.

In addition all SAEs will be recorded on the SAE Report Form. Study centres are instructed to report all SAEs and AEs of special interest (ie, infusion-related reactions and allergic reactions to study drug grade 3 or higher, cytokine release syndrome, overdoses) to United Bio Source within 24 hours using the study-specific SAE report form.

Infusion-related reactions and allergic reactions to study drug grade 3 or higher, or cytokine release syndrome, which are AEs of special interest in this study, should be reported along with their respective symptoms (eg, hives, chill, and fever for infusion reaction). Equally, for overdoses the symptoms caused by the overdose should be reported. If an AE has already been reported, it is not necessary to report each individual sign and symptom of that AE as a separate AE. For example, if myocardial infarction is reported as an AE, there is no need to report elevated creatine phosphokinase and abnormal ECG, or other related signs, symptoms, or laboratory values as separate AEs. However, if both occurred in isolation and myocardial infarction was not diagnosed, then each event would be reported as an AE.

All nonserious AEs must be followed up for a final outcome. An outcome of “unknown” is not considered to be an acceptable final outcome. An outcome of “not yet resolved” is an acceptable final outcome for nonserious AEs at the end of a patient’s participation in a study. All SAEs must be followed up for a final outcome until resolution or, if resolution becomes unlikely, until stabilization or death. The follow-up for SAEs that are a progression of NHL only until the end of a patient’s participation in a study is acceptable. This includes obtaining information on recovery and any sequelae and, in case of a fatal outcome, the cause of death.

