11.1 Adverse Events

The primary safety endpoint is the incidence and severity of adverse events (AEs). This endpoint will be determined based on the Safety Population. If not specified otherwise, the adverse events summary and overall table will be displayed overall, by each NHL subtype, and for the combined group of FL and other indolent NHL.

All adverse events (AEs) and serious adverse events (SAEs) will be coded using the Medical Dictionary for Regulatory Activities (MedDRA), Version 20.1.

Treatment emergent AEs are defined as AEs occurring or worsening after the start (date and time) of the first study treatment and up to 30 days after the last study treatment including all treatment cycles (treatment emergent period). However, adverse events occurring or worsening later than 30 days after the last treatment are defined as treatment emergent if these are considered to be related to the study drug.

If the start date and time of an AE are partially or completely missing, the AE will be assumed to be treatment-emergent if it cannot be definitely shown that the AE did not occur or worsen

during the treatment emergent period (worst case approach). Missing dates and times will not be replaced.

Thus, the following approach will be taken:

- If the start time of an AE is missing but the start date is complete, an AE will only be excluded from treatment emergent AEs if start day is before day of first treatment or start day is after end day of treatment emergent period.
- If start time and day are missing but the start month is complete, an AE will only be excluded from treatment emergent AEs if start month is before month of first treatment or start month is after end month of treatment emergent period or if stop date/time is before start of first treatment.
- If start day and months are missing but the start year is complete, an AE will only be excluded from treatment emergent AEs if start year is before year of first treatment or if start year is after end year of treatment emergent period or if stop date/time is before start of first treatment.
- If start date is completely missing, an AE will not be excluded from treatment-emergent AEs unless the stop date/time is before start of first treatment.

Time from first treatment to onset of AE [days] will be calculated for complete dates only and will be included in listings.

An AE summary table will be presented showing the incidence and frequency of any

- Treatment-emergent AEs (TEAEs)

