In the AE listings, AEs that started prior to the administration of any study drug will be flagged as pre-treatment AEs. AEs that start 30 days after the last study treatment including all treatment cycles will be flagged as post-treatment AEs.

Special AE summary listing displaying details of the event(s) captured on the eCRF in a compact format will be provided for

- AEs leading to death
- AEs leading to discontinuation of MOR00208
- AEs of toxicity grade 3 or higher
- Infusion related TEAEs
- Serious Adverse Events
- Death cases (irrespective of death due to disease progression or other reason)

Serious adverse event reconciliation will be performed as detailed in the SAE reconciliation plan.

The number and percent of patients with at least one pretreatment AE will be summarized by NHL subtype and by system organ class and preferred term.

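### SAP 11.1's rule for AEs with an incomplete start, applied as written, excludes late drug-related AEs that its own definition counts as treatment-emergent

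*SAP*

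**What the plan says.** SAP 11.1 (Adverse Events) gives a definition and then a rule for incomplete dates.

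The definition has two limbs. The first is "Treatment emergent AEs are defined as AEs occurring or worsening after the start (date and time) of the first study treatment", running to 30 days after the last dose; this span is named the treatment emergent period. The second limb goes beyond the period and concerns AEs attributed to study drug: "adverse events occurring or worsening later than 30 days after the last treatment are defined as treatment emergent if these are considered to be related".

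For AEs with a partly or wholly missing start, the SAP announces a worst-case principle: the AE is treated as treatment-emergent "if it cannot be definitely shown that the AE did not occur or worsen" in the treatment emergent period. Four bullets then set out the approach:

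- Time missing, date complete: excluded only if "start day is before day of first treatment or start day is after end day of treatment emergent period".
- Time and day missing: excluded only if "start month is before month of first treatment or start month is after end month of treatment emergent period", or if the AE stopped before first treatment.
- Day and month missing: the same tests by calendar year.
- Start wholly missing: excluded only if the AE stopped before first treatment.

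Protocol 11.1 limits what reaches the database after 30 days: "Thereafter only AEs assessed as related should be recorded".

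**The concern.** The second limb of the definition depends on relatedness and has no end date. The first three bullets test the start against the end of the treatment emergent period and never look at relatedness. The worst-case sentence above them also refers only to the period, so the second limb appears not to have been carried into the rule.

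A missing clock time on a fully dated AE is enough to bring the first bullet into play, although clock time has no bearing on an event that starts weeks after the last dose. Whether the event counts would then depend on how completely a form was filled in.

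Incidence and severity of AEs is a secondary endpoint (Protocol 7.3, SAP 2.2.2) and is called the primary safety endpoint in SAP 11.1. Protocol 4.2.2 names hepatitis B reactivation, progressive multifocal leukoencephalopathy and infections among the anticipated risks. Protocol 10.5 asks for anti-HBc-positive patients to be followed for reactivation after the End of Study visit. A related event first seen off treatment is what the second limb is there to keep.

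**Working it through.** The plan attaches no figure to this point, so there is nothing to reproduce. The check applies the definition and the four bullets to the same AEs.

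Inputs: the two limbs of the definition and the bullets from SAP 11.1; the recording rule from Protocol 11.1. The dates are illustrative assumptions: first dose 10 March 2014, last dose 28 May 2014. The treatment emergent period then ends on 28 May + 30 days = 27 June 2014.

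**Late AEs**

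| AE | By definition | Time blank | Day blank | Month blank | Start wholly missing |
|---|---|---|---|---|---|
| Related, starts 12 July 2014 (last dose + 45 days) | TEAE | excluded | excluded | kept | kept |
| Related, starts 5 September 2014 (+ 100 days) | TEAE | excluded | excluded | kept | kept |
| Related, starts 3 February 2015 (next year) | TEAE | excluded | excluded | excluded | kept |
| Unrelated, starts 5 September 2014 | not a TEAE | excluded | excluded | kept | kept |

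In the first row, 12 July is after 27 June, so the first bullet excludes the AE. July is after June, so the second bullet excludes it. The year 2014 is not after 2014, so the third bullet keeps it. With a complete date and time no bullet applies, and the definition makes the AE a TEAE.

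The conflict is therefore confined to the first three bullets. A related AE starting in the month (or year) in which the period ends is kept when the day (or month) is missing.

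The unrelated AE in the last row should not be in the database, because Protocol 11.1 records only related AEs after 30 days. Where that rule is followed, the clauses on starts after the period can act only on AEs that the second limb makes treatment-emergent.

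**Pre-dose AEs**

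| AE | By definition | Time blank | Day blank | Month blank | Start wholly missing |
|---|---|---|---|---|---|
| Starts 3 March 2014, worsens 20 March | TEAE | excluded | kept | kept | kept |
| Starts 24 February 2014, worsens 20 March | TEAE | excluded | excluded | kept | kept |
| Starts 24 December 2013, worsens 20 March | TEAE | excluded | excluded | excluded | kept |
| Starts 24 February 2014, resolved 1 March, no worsening | not a TEAE | excluded | excluded | excluded | excluded |

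The last row is a control, and definition and rule agree on it throughout. The first three rows conflict only if the worsening stays on the record that carries the pre-dose start date.

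**The case against.** The best defence is textual. The bullets say when an AE may be excluded, which can be read as a necessary condition only. They follow from a sentence about the treatment emergent period, so they might settle membership of the period and leave the second limb to add late related AEs back. That reading is possible. But the bullets are introduced as the approach to be taken, and a programmer would code them as the exclusion test. If the override is intended, one clause would say so.

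The exposed group is also limited, and this stands. Patients without at least SD after Cycle 2 have their End of Study visit 4 weeks (± 2 days) after the last Cycle 2 dose (Protocol 10.5), about when the 30 days end. For patients on maintenance, the period extends with each dose. The clause mainly concerns patients followed off treatment.

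A reader might infer three stronger points that the documents do not support.

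- *Worsened pre-dose AEs are lost.* Protocol 10.8.1 makes an increase in frequency or intensity of a pre-existing condition an AE in itself, and Protocol 10.8.2 has worsening examination findings recorded as AEs. If worsening gets its own record and start date, nothing is lost. Protocol 11 also has changes in severity followed within a detected AE, so the documents do not settle the matter.
- *The listings contradict the definition.* The SAP says "AEs that start 30 days after the last study treatment including all treatment cycles will be flagged as post-treatment AEs". That flag describes timing. It does not say that a flagged AE is not a TEAE, and a late related AE can be both.
- *A set number of percentage points is lost.* No count of late related AEs or blank times is given. Incidence counts patients with at least one TEAE, so a patient with another related TEAE is already in the overall rate. Infusion reactions alone occurred in 12 of 21 (57.1%) Phase I patients (Protocol 4.2.2). One patient over the cohort size would be only an upper bound for the overall related-TEAE rate.

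**Conclusion.** The point holds for late related AEs. Applied as written, the first three bullets exclude events that the definition in the same section includes, and a blank clock time is enough to cause it.

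The size is unknown. It depends on how many related AEs start more than 30 days after the last dose and how many of those have an incomplete start. The direction is known: this error can only lower the TEAE, related-TEAE and Grade 3 or higher TEAE tables, which runs against a rule described as worst case. The events are not hidden, because SAP 11.1 also lists all AEs, and separately SAEs and AEs of Grade 3 or higher, without a TEAE restriction.

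The conclusion assumes that the bullets are programmed as the exclusion test. The part on worsening is conditional on how worsening is recorded.

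**What to change.** In each of the first three bullets of SAP 11.1, limit the exclusion for a start after the end of the treatment emergent period to AEs not considered related to study drug. The fourth bullet needs no change.

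State in the SAP how worsening of a pre-dose AE is recorded. If it stays on the original record, also limit the exclusion for a start before first treatment to AEs that did not worsen after first treatment. If worsening is entered as a new AE with its own start, no change is needed there.

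The cost is a few words and a programming condition. Relationship to study drug is already collected, and Protocol 10.8.1 treats an AE with no stated relationship as related, so the condition can always be evaluated. Some TEAE counts may rise. The worsening condition, if needed, requires that a worsening date can be read from the AE record.

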8.4 Procedures for Enrolment

A fully signed informed consent must be available before the start of screening activities.

Patients who are able to understand the study but unable to read or write may be consented in accordance with the local legislation, e.g. written confirmation by a witness.

Enrolment to treatment will be performed after all inclusion and exclusion criteria have been confirmed and the patient is found to be eligible.

Patients can be re-screened once if since the last visit (either screening or baseline visit) at least four weeks have elapsed.

In cases of re-screening, patients need to be reconsented and a new patient number will be assigned.

Re-screening procedures

Patients can be re-screened at the discretion of the investigator under certain circumstances. Re-screening is restricted to one attempt per patient and may be performed only if one of the following criteria is met:

- If the inclusion of a patient who has already consented and who met all the inclusion and has met none of the exclusion criteria is delayed due to an unexpected change in the patient's personal situation (e.g. family issues),
- If a patient previously failed to be eligible due to any event (e.g. planned surgery) that has since been resolved,
- If the allowed concomitant medication doses have stabilized,
- If laboratory values that prevented the inclusion of a patient based on the first screening attempt have changed to satisfy the inclusion and exclusion criteria outlined in the currently valid study protocol,
- If a patient who previously failed screening becomes eligible for the study, based on a change in the inclusion and exclusion criteria following a protocol amendment.
- If a patient failed screening due to non-progressed/non-relapsed disease at the time of screening and later is clinically diagnosed as having progressed/relapsed.

NOTE: A patient should only be re-screened if there is a clear indication that the patient may be eligible according to the currently valid study protocol.

In these cases, if previous screening activities were discontinued and enrollment did not occur, the following procedure should be implemented:

- the patient must sign and date a new Informed Consent Form as part of the screening procedure,
- the patient will receive a new unique inclusion/identification number and, in case of eligibility, a new unique number via the IWRS,
- a new Case Report Form (CRF) will be completed,

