- the patient will be documented as re-screened in the source documents, and
- recording of medical histories, physical examinations, prior NHL treatments, adverse events, and concurrent medications will be transcribed from the previously used to the new CRF if the conditions and medications still apply to the current status of the

re-screened patient as documented in the source documents. All screening procedures must be completed again.

A re-screened patient can be enrolled if all current inclusion criteria are met and none of the exclusion criteria are met.

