10.8.1 Adverse Events

An adverse event (AE) is defined as any untoward medical occurrence in a patient or clinical subject administered a medicinal product, which does not necessarily have a causal relationship to this treatment.

An AE can therefore be any unfavourable and unintended sign (including an abnormal laboratory finding), symptom, or disease temporally associated with the use of a study drug, whether or not it is considered related to that study drug.

Temporally associated means after signing the informed consent form until 30 days after last administration of the study drug.

For screening failure patients only SAEs will be recorded in the eCRF.

AEs include any clinically significant deterioration of a patient's medical status after the signing of the informed consent form. Also an increase in frequency or intensity of a preexisting episodic event or conditions and events resulting from protocol mandated procedure (eg, invasive procedures) fall under the definition of AE. In addition, overdoses (defined as exceeding planned dose by more than 10%) should be recorded as AEs.

As far as possible, each AE should be evaluated to determine the following:

- Relationship to study drug (suspected/not suspected)
- Duration (start and end date or if continuing at end of study)
- Intensity: The intensity of all AEs will be graded as mild, moderate, or severe using the following definitions:
 - Mild: Tolerable
 - Moderate: Interferes with normal activity
 - Severe: Incapacitating (causes inability to perform usual activity or work)

- Toxicity grade: The toxicity grade of AEs will be graded according to the NCI-CTC (CTCAE version 4.0 of May 28, 2009) using the following definitions:
 - Grade 1: Mild; asymptomatic or mild symptoms; clinical or diagnostic observations only; intervention not indicated.
 - Grade 2: Moderate; minimal, local or noninvasive intervention indicated; limiting age-appropriate instrumental activities of daily living (refers to preparing meals, shopping for groceries or clothes, using the telephone, managing money, etc.).
 - Grade 3: Severe or medically significant but not immediately life-threatening; hospitalization or prolongation of hospitalization indicated; disabling; limiting self-care activities of daily living.
 - Grade 4: Life-threatening consequences; urgent intervention indicated.
 - Grade 5: Death related to AE.
- Outcome

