8. STUDY PATIENTS AND DEMOGRAPHICS

8.1 Disposition of Patients and Treatment Discontinuation

The following will be summarized by study population (i.e., NHL subtype) for all patients who provided an informed consent for study participation:

CONFIDENTIAL

03 April 2019

AD-ST-33.02 8 April 2011

Statistical Analysis Plan Final Version 4.0

- Number (%) of patients enrolled (defined as having completed the Informed Consent eCRF page)
- Number (%) of patients screened
- Number (%) of screen failures including the reasons for being screen failures
- Number (%) of patients treated (as per IRT information)
- Number (%) of patients who discontinued in Cycle 1 or Cycle 2 (considering all discontinuations during the Cycles including those at the end of Cycle 2, i.e., C2D28), including the reason for discontinuation
- Number of patients who discontinued before completing Cycle 2 including the reason for discontinuation
- Number of patients completing Cycle 2
- Number of patients completing the first 2 Cycles without proceeding to Cycle 3 (i.e., PD or SD at the end of Cycle 2), including the reason for discontinuation
- Number of patients who completed Cycle 2 and entered Cycle 3 (i.e., patients who reached PR, or CR by the end of Cycle 2)
- Number of patients who discontinued in Cycle 3 (considering all discontinuations that happened in Cycle 3 including those at the end of Cycle 3, i.e., C3D28), including the reason for discontinuation
- Number of patients who discontinued in Cycle 1 or 2 or 3 (considering all discontinuations that happened during Cycle 1, 2, 3 including those at the end of Cycle 3, i.e., C3D28), including the reason for discontinuation
- Number of patients who entered the maintenance treatment phase (i.e., treatment after Cycle 3)
- Number of patients who discontinued during the maintenance treatment phase including the reason for discontinuation
-
- Number of patients still on treatment (i.e., ongoing at data cut-off; the information will be derived from entries in the IRT system)
- Number (%) of patients screened, and number (%) of screen failures including the reason for screen failure.

- Number (%) of patients screened, and number (%) of screen failures by center.

These summaries will be presented for the population of screened patients. The disposition summary will additionally be presented for all patients enrolled, including screening failures.

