- Serious Adverse Events (SAEs)
- Serious Adverse Events (SAEs) related to MOR00208
- MOR00208-related TEAEs
- MOR00208-related TEAEs by toxicity (according to NCI-CTC toxicity criteria)
- MOR00208-related TEAEs by severity
- Infusion related TEAEs
- TEAEs leading to any action on MOR00208
- TEAEs leading to discontinuation of MOR00208
- TEAEs leading to death

Statistical Analysis Plan Final Version 4.0

The incidence refers to the number and percentage of patient with at least one TEAE of the specified type and the frequency to the number of AEs.

The analyses by toxicity will be based on the NCI-CTC grade (per National Cancer Institute Common Toxicity Criteria, version 4.0). If the NCI-CTC grade is not available, this will be analyzed as “Missing”.

Summaries of incidence rates (number and percentage of patients) and frequencies (number of AEs) of individual TEAEs by MedDRA System Organ Class (SOC) and Preferred Term will be prepared overall and by NHL subtype. Such summaries will be displayed for all

- TEAEs
- TEAEs by toxicity according NCT-CTC
- TEAEs by severity
- TEAEs suspected to be related to MOR00208
- TEAEs leading to discontinuation of MOR00208
- Infusion related TEAEs
- Cytokine release syndromes
- Treatment-Emergent Serious Adverse Events
- TEAEs suspected to be related to MOR00208
- Serious Adverse Events suspected to be related to MOR00208 (Serious Adverse Reactions)
- TEAEs of toxicity grade 3 or higher
- MOR00208-related TEAEs of toxicity grade 3 or higher
- TEAEs of special interest (ie, infusion-related reactions of grade 3 or higher, cytokine release syndrome, allergic reaction to MOR00208 of grade 3 or higher and overdoses)
- Haematological Treatment Emergent Adverse Events
- Overdoses (defined as exceeding planned dose by more than 10%)
- Death cases (irrespective of death due to progressive disease or other reason)
- Pre-treatment AEs (based on all Screened Patients instead of the Safety Population)

A summary of all TEAEs will also be provided by FcγR polymorphisms.

In these summaries each patient will be counted only once within each preferred term to calculate the incidences.

AE listings of all adverse events with the following details will be provided for

- AEs – details
- AEs – action taken
- AEs – coding details

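### The pre-treatment AE table divides by all screened patients, although non-serious AEs of screening failures are not recorded in the eCRF

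*SAP*

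**What the plan says.** **Denominator.** In the list of AE summaries by system organ class and preferred term, SAP 11.1 includes "Pre-treatment AEs (based on all Screened Patients instead of the Safety Population". The end of the same section plans the pre-treatment summary again and names no base. SAP 6 does not define a screened population.

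**Data capture.** Protocol 10.8.1: "For screening failure patients only SAEs will be recorded in the eCRF". Protocol 11.1 agrees: "For screening failure patients the non-serious adverse events will not be recorded in the e-CRF but only in the patient’s medical records".

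**General rule.** Protocol 14.5 assigns all safety analyses to the Safety Population, meaning dosed patients. SAP 7.1 has the same general rule. Protocol 14.7.1 plans a pre-treatment AE summary and gives no exception for it. SAP 12 lists three changes from the protocol: the PK population, ORR by central read, and the CD19 endpoint. The all-screened base is not among them.

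**Re-screening.** Protocol 8.4: "In cases of re-screening, patients need to be reconsented and a new patient number will be assigned". In addition, "a new Case Report Form (CRF) will be completed", and adverse events that still apply are carried over to it. SAP 8.1 tabulates patients enrolled, screened, screen-failed and treated, with no rule for a person who holds two numbers.

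**The concern.** A percentage is interpretable only if everyone in the denominator could have contributed to the numerator. Here one group, the screening failures, is in the denominator by instruction, while its non-serious events are kept out of the database by instruction. The table would report events that were not collected as events that did not occur.

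What is at stake is a descriptive safety table. Its percentages for non-serious pre-treatment events would be too low, by an amount that depends on how many patients fail screening and not on anything about the patients' health.

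**Working it through.** The documents state no pre-treatment AE rate, no screen-failure fraction and no number of re-screened patients, so there is no planned figure to reproduce.

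**Inputs**
- Denominator: all screened patients (SAP 11.1).
- Numerator, non-serious events: only patients who did not fail screening (Protocol 10.8.1, 11.1).
- Numerator, serious events: everyone screened (same sections).
- Treated patients T: 120, the upper end of the planned 40 to 120 (SAP 5), used for scale only.
- Screen-failure fraction f: assumed 10%, 20%, 30%.
- True risk p of a non-serious pre-treatment AE: assumed 20%.
- Assumed: everyone who passes screening is dosed.

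**Formula.** With N persons screened, (1 − f)N have all their AEs recorded, and p(1 − f)N of these have a non-serious event.

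- Displayed rate = p(1 − f)N / N = p(1 − f).
- Rate on the Safety Population = p(1 − f)N / ((1 − f)N) = p.
- Relative understatement = 1 − (1 − f) = f.

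The relative understatement depends on neither p nor T.

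**Numbers.** With T = 120 and p = 20%, 24 patients have a recorded event. Screened = 120 / (1 − f).

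| f (assumed) | Screened | Displayed rate | Rate on Safety Population | Relative understatement |
|---|---|---|---|---|
| 10% | 133.3 | 24/133.3 = 18.0% | 24/120 = 20.0% | 10% |
| 20% | 150 | 24/150 = 16.0% | 20.0% | 20% |
| 30% | 171.4 | 24/171.4 = 14.0% | 20.0% | 30% |

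**Serious events.** They are recorded for screening failures too, so the factor does not apply, and all screened patients are the right base. A line for any pre-treatment AE mixes the two kinds of event and is therefore understated by f or somewhat less.

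**Re-screening (conditional).** Take f = 20% and T = 120, and assume that 10% of treated patients (12 persons) had an earlier failed attempt. If tables were programmed by ID and not by person:
- screened = 150 + 12 = 162 instead of 150;
- screen failures = 30 + 12 = 42 instead of 30, a share of 42/162 = 25.9% instead of 30/150 = 20.0%;
- displayed AE rate = 24/162 = 14.8% instead of 16.0%.

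If IDs are linked, none of these shifts occurs.

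**What does not move.** Treatment-emergent AE tables use the Safety Population (SAP 6, 11.1). ORR uses the ITT Population, which is also restricted to dosed patients. The futility rule counts responders. Re-screening applies only where enrolment did not occur (Protocol 8.4), and withdrawn patients may not re-enter (Protocol 9.11.1), so a person can be dosed under only one ID.

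**The case against.** The all-screened base is a stated choice and has a purpose: every consented patient is at risk of an event from a screening procedure, and this base keeps the serious events of screening failures in view. Moving the whole table to the Safety Population would lose them. Counts accompany the percentages, the number treated is reported, and listings flag pre-treatment AEs, so a careful reader could rebuild the rate. A footnote on SAE-only capture might seem enough.

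The purpose stands for serious events, and the fix keeps that table. For non-serious events the argument fails, because their absence in screening failures is a recording rule. A footnote would disclose the bias without removing it. The table's counts alone do not let a reader undo it either, since serious events of screening failures and all events of treated patients share one numerator.

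Four stronger readings are tempting, and the documents do not support them.

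- **AE rates in general are wrong.** Only the pre-treatment table is affected.
- **Re-screened patients will be counted twice.** SAP 8.1 speaks of patients, not IDs. Protocol 8.4 requires re-screened status in the source documents and does not exclude it elsewhere; whether the database links the two IDs is not stated. What is missing is a rule. Copied events add little duplication: only those that still apply are copied, and a failed first ID should hold only serious events, so duplication is confined mainly to ongoing SAEs. SAP 11.1 also refers to a separate SAE reconciliation plan.
- **The consent-based count of enrolled patients will misstate the trial's size.** SAP 8.1 has "Number (%) of patients enrolled (defined as having completed the Informed Consent eCRF page", whereas Protocol 8.4 places enrolment to treatment after eligibility is confirmed. This is a difference of terminology: the SAP states its definition and reports treated patients separately, and that count can be compared with 40 to 120.
- **The table is the benchmark for treatment-emergent events.** Neither document gives it that role. Screening lasts up to 21 days, against 8 to 12 weeks or more of treatment plus 30 days, so raw incidences would not be comparable on any base.

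**Conclusion.** The mismatch is real and follows from the text alone: the SAP's denominator includes patients whose non-serious events the protocol keeps out of the database. For non-serious pre-treatment AEs, the displayed incidence is the rate in patients with full recording times (1 − screen-failure fraction). That is 10% to 30% too low in relative terms if 10% to 30% of screened patients fail; this range is assumed. The factor also assumes that everyone who passes screening is dosed. The direction of the bias needs no figure beyond there being some screening failures.

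The base is also an unlisted departure from Protocol 14.5. The consequence is small: one descriptive table, with no effect on treatment-emergent AEs, ORR or the decision to open Stage 2. Re-screening adds only a missing counting rule, not a demonstrated error.

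**What to change.** 1. **SAP 11.1:** present all pre-treatment AEs on the Safety Population, and present pre-treatment SAEs separately on all screened patients. Apply the same bases to the summary repeated at the end of the section.
2. **SAP 6:** define the screened population.
3. **SAP 12:** list the all-screened base of the SAE table as a change from Protocol 14.5.
4. **SAP 8.1 (minor clarification):** state that a re-screened patient is counted once, by the outcome of the last screening attempt.

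The cost is one extra small table and a few sentences of SAP text. The last item also needs a link between a re-screened patient's two IDs, from site re-screening records if the database holds none. No new patient data are required.
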